8 STUDY PROCEDURES BY VISIT

The schedules of study assessments ([Table 5–1](#) and [Table 5–2](#)) provide a general overview of study assessments. A list of procedures to be completed at each visit is provided in the sections that follow.

- Visit windows of ± 7 days on either side of the scheduled dosing are permitted for all visits other than the SFU Visit (see below); however, the Investigator should try to keep the subjects on the original dosing schedule. The window of ± 7 days is relative to the first dose (AS0009 entry) and applicable for all subsequent visits. Changes to the dosing schedule outside of the 14-day window must be discussed with the Medical Monitor.
- The minimum time between doses should be no less than 21 days and no more than 35 days for Q4W dosing.
- For the SFU Visit (20 weeks after the last dose), the visit should occur no more than 3 days prior to the scheduled visit date and within 7 days after the scheduled visit date (-3 days/+7 days).

The Investigator should make efforts to maintain the original visit schedule. Changes to the dosing schedule outside of the allowed windows must be discussed with the Medical Monitor and may result in subject withdrawal.

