ASQoL	X ^f		X		X		X		X		X		X		X		X	
BASDAI	X ^f		X		X		X		X		X		X		X		X	
BASFI	X ^f		X		X		X		X		X		X		X		X	
SF-36	X ^f		X		X		X		X		X		X		X		X	
PGADA	X ^f		X		X		X		X		X		X		X		X	
Total and nocturnal spinal pain	X ^f		X		X		X		X		X		X		X		X	
TB questionnaire	X ^f		X		X		X		X		X		X		X		X	
Vital signs (pulse, temperature, BP) ^g	X ^{e,f}	X	X		X		X		X		X		X		X		X	
Body weight	X ^f		X		X		X		X		X		X		X		X	
Physical examination ^h	X ^f								X								X	
MASES	X ^f		X		X		X		X				X				X	
BASMI	X ^f								X								X	
ECG	X ^f								X								X	

Table 2–1: Schedule of study assessments (Week 1 through Week 104)

Protocol activity	Treatment Period																		
	EV ^b	4	12	16	24	28	36	40	48	52	60	64	72	76	84	88	96	100	
		8	20		32		44		56		68		80		92		104		
Visit ^a	1	2/3	4	H ^c	5	H ^c	6	H ^c	7	H ^c	8	H ^c	9	H ^c	10	H ^c	11	H ^c	
Hematology/biochemistry/urine pregnancy ^{i, j}	X ^f		X		X		X		X		X		X		X		X		
Blood Sample for CRP ⁱ	X ^f		X		X		X		X		X		X		X		X		
Blood sample for bimekizumab plasma concentrations ^j	X ^f		X		X		X		X				X				X		
Blood sample for anti-bimekizumab antibodies ^j	X ^f		X		X		X		X				X				X		
IGRA TB test ^k	X								X									X	
IXRS	X	X	X		X		X		X				X		X		X		X
Bimekizumab administration	X	X	X	X	X	X	X	X	X	X	X	X	X	X	X	X	X	X	

ASQoL=Ankylosing Spondylitis Quality of Life; BASDAI=Bath Ankylosing Spondylitis Disease Activity Index; BASFI=Bath Ankylosing Spondylitis Functional Index; BASMI=Bath Ankylosing Spondylitis Metrology Index; BASFI=Bath Ankylosing Spondylitis Metrology Index; BP=blood pressure; CRP=C-reactive protein; ECG=electrocardiogram; eC SSRS=electronic Columbia-Suicide Severity Rating Scale; EV=Entry Visit; H=home; HADS=Hospital Anxiety and Depression Scale; IGRA=interferon gamma release assay; IMP: investigational medicinal product; IXRS=interactive voice or web response system; MASES= Maastricht Ankylosing Spondylitis Enthesitis Index; PGADA=Patient's Global Assessment of Disease Activity; SF 36=36 item short form health survey; SFU=Safety Follow Up; TB=tuberculosis;

Note: The SFU Visit will occur 20 weeks after the last dose of IMP.

^a Visit windows are ± 7 days from the scheduled visit day (relative to the first dose) with a minimum of 21 days and a maximum of 35 days in between doses at all visits except the SFU Visit which should occur no more than 3 days prior the scheduled visit date and within 7 days after the scheduled visit date (-3 days /+7 days).

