- Action taken with IMP: dose not changed, dose reduced, dose increased, drug temporarily, interrupted, drug permanently withdrawn or not applicable
- Outcome: resolving, not resolved, resolved, resolved with sequelae, worsened, fatal or unknown

AEs (including SAEs) are characterized as either non-treatment-emergent or treatment emergent according to the following criteria:

- Non-treatment emergent AEs are those with onset date after a 140-day period after the end date of study medication.
 - Any AE occurring more than 140 days after the last administration of study medication in AS0008 and prior to the first administration of study medication in AS0009 will also be considered as non-treatment emergent, and will therefore be excluded from the summary tables. Such events will be included in the listings.
- TEAEs are those with onset date on or after the start date of study medication in AS0009.
- Events that were ongoing at the end of AS0008 will have their treatment-emergent status taken from the AS0008 database.

For all AEs the following variables will be calculated (see [Section 10.2.1](#)):

- Duration.
- Time since first bimekizumab dose.
- Time since last/latest bimekizumab dose.

AE summaries will, in general, include only events with onset on or after the start date of study treatment in AS0009. Certain displays will be repeated including all AEs in AS0008 (with the exception of those with onset during placebo treatment) and AS0009 as outlined below. These displays will include only subjects from AS0008 who were enrolled in AS0009.

In general, the attributes of these events (for AEs that started and were resolved in AS0008) will be taken from the AS0008 database. However, the identification of Safety Topics of Interest will be made across all events in AS0008 and AS0009 using the criteria defined in this SAP.

For events which were ongoing at the end of AS0008, the following rules will be implemented:

- Onset date (and derived variables) will be taken from the AS0008 database
- End date, outcome, actions taken and seriousness will be taken from the AS0009 database.
- In order to ensure that AEs are not duplicated in the outputs these will be merged across the studies by Subject ID, verbatim term (AETERM), dictionary-derived term (AEDECOD), start date (AESTDTC), relationship (AEREL) and severity (AESEV) to create one record for the specific event.

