Creatinine ^a	High	umol/L	>1-1.5 x Baseline or >ULN-1.5 x ULN	>1.5-3.0 x Baseline or >1.5 – 3.0 x ULN	>3.0 x Baseline or >3.0 – 6.0 x ULN	>6.0 x ULN
Sodium	Low	mmol/L	130-<LLN	N/A	120-<130	<120
Sodium	High	mmol/L	>ULN-150	>150-155	>155-160	>160
Potassium ^b	Low	mmol/L	3.0-<LLN	3.0-<LLN	2.5-<3.0	<2.5
Potassium	High	mmol/L	>ULN-5.5	>5.5-6.0	>6.0-7.0	>7.0
Calcium	Low	mmol/L	2.0-<LLN	1.75-<2.0	1.5-<1.75	<1.5
Calcium	High	mmol/L	>ULN-2.9	>2.9-3.1	>3.1-3.4	>3.4
Magnesium	Low	mmol/L	0.5-<LLN	0.4-<0.5	0.3-<0.4	<0.3
Magnesium	High	mmol/L	>ULN-1.23	N/A	>1.23-3.30	>3.30
Cholesterol	High	mmol/L	>ULN-7.75	>7.75-10.34	>10.34-12.92	>12.92

LLN=lower limit of normal, ULN=upper limit of normal.

^a The CTCAE grade definitions for creatinine are based on the logical OR; the highest applicable CTCAE grade should be assigned to a specific creatinine value.

^b Note that subjects who meet the decreased potassium criterion of $3.0 < \text{LLN}$, which is specified as the decreased potassium lab criterion for both CTCAE Grade 1 and Grade 2, will be counted as Grade 2.

The number and percentage of subjects with elevated liver function tests will be presented by treatment group at completion of AS0008 and overall, using on-treatment assessments (excluding any measurements that occurred prior to the first administration of study medication in AS0009 or more than 140 days after the last administration of study medication) from all visits in AS0009 including those at AS0009 Laboratory Baseline, unscheduled, ET and SFU visits. Assessments performed at both central and local laboratories will be included. Each subject will be counted once only. The number and percentage of subjects in the following categories at any time during the study will be presented:

- AST: $>3\times\text{ULN}$, $>5\times\text{ULN}$, $>8\times\text{ULN}$, $>10\times\text{ULN}$, $>20\times\text{ULN}$.
- ALT: $>3\times\text{ULN}$, $>5\times\text{ULN}$, $>8\times\text{ULN}$, $>10\times\text{ULN}$, $>20\times\text{ULN}$.
- AST or ALT: $>3\times\text{ULN}$, $>5\times\text{ULN}$, $>8\times\text{ULN}$, $>10\times\text{ULN}$, $>20\times\text{ULN}$.
- Total bilirubin: $>1.5\times\text{ULN}$, $>2\times\text{ULN}$.
- ALP: $>1.5\times\text{ULN}$.

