The number and percentage of subjects who meet Hy's Law criteria ([Section 10.2.3](#)) will be presented by treatment group at completion of AS0008 and overall, using on-treatment assessments (excluding any measurements that occurred prior to the first administration of study medication in AS0009 or more than 140 days after the last administration of study medication) from all visits including those at AS0009 Laboratory Baseline, unscheduled, ET and SFU visits. Hy's Law criteria are displayed below:

- (AST $\geq 3\times\text{ULN}$ or ALT $\geq 3\times\text{ULN}$) and Total Bilirubin $\geq 2\times\text{ULN}$ in the absence of ALP $\geq 2\times\text{ULN}$.

To meet the above criteria, a subject must experience the elevation in total bilirubin and ALT or AST and the absence of ALP elevation at the same visit.

All hematology and biochemistry laboratory data (except CRP) will be listed, including age, sex, race, weight, changes from AS0009 Laboratory Baseline for numeric variables, flags for measurements outside the normal ranges, flags for measurements meeting the criteria for each CTCAE grade ([Table 10–9](#) and [Table 10–10](#)) the relative study day, a flag for whether the test was not done and a flag for whether the subject was fasting.

CRP will be listed separately as described in [Section 8](#).

Values that are below the lower limit of the reference range will be flagged as 'L' (low) and values that are above the upper limit of the reference range will be flagged as 'H' (high) in listings. Values that meet the criteria for each CTCAE grade will be flagged as 'LGrx' or 'HGrx' accordingly.

The markedly abnormal laboratory results will be listed separately.

Any additional laboratory assessments performed during the study will be listed separately.

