10.5.3 Other safety variables

Assessment of Tuberculosis

Scheduled TB laboratory test results will be included in the laboratory data listings. Results of unscheduled TB testing at local laboratories will be listed separately. The response to the first question of the 'Evaluation of signs and symptoms of tuberculosis' questionnaire will be listed.

[figure not shown]
Electronic Columbia Suicide Severity Rating Scale

The electronic Columbia-Suicide Severity Rating Scale (eC-SSRS) is a standardized and validated instrument developed for the assessment of the severity and frequency of suicidal ideation and behavior ([Posner et al, 2011](#); [Mundt et al, 2010](#)).

Suicidal ideation is defined as an event in any of the following 5 categories:

Suicidal behavior is defined as an event in any of the following 4 categories:

Suicidal ideation or behavior is defined as an event in any of the above 9 categories.

Self-injurious behavior without suicidal intent will also be reported.

The eC-SSRS can be administered to assess suicidal ideation and behavior over a lifetime, or since the last time it was assessed. The intent in this OLE study was to assess suicidal ideation and behavior since the last time it was assessed and refer back to the lifetime assessment conducted at the start of AS0008. However, some subjects completed the 'lifetime' assessment (in error) at one or more visits in AS0009 and recorded positive responses to some questions. Based on a review of their original lifetime assessment in AS0008, these positive responses are

not considered to represent a change in suicidal ideation and behavior during the study. The summary tables will include only the ‘since last assessment’ responses; all responses will be listed.

The incidence of subjects with suicidal ideation, suicidal behavior, suicidal ideation or behavior and self-injurious behavior at least once for any on-treatment assessment (including unscheduled assessments, but excluding any measurements that occurred prior to the first administration of study medication in AS0009 or more than 140 days after the last administration of study medication) during AS0009, will be summarized by treatment group at completion of AS0008.

eC-SSRS data will be listed.

Health Care Provider Consultations

Out-patient non-protocol health care provider consultations will be listed.

Extra-articular assessments

Extra-articular assessments performed after the AS0009 EV will be listed separately for the SS.

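### The SAP's on-treatment laboratory, blood-pressure and eC-SSRS tables stop at day 140, so on-time Safety Follow-up results on 7 of the 11 permitted days are left out

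*SAP*

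**What the plan says.** **Timing of the visit.** The notes to the SAP schedule tables (section 2.3) state: "The SFU Visit will occur 20 weeks after the last dose of IMP". Protocol section 8 treats the visit as on time if it occurs "no more than 3 days prior to the scheduled visit date and within 7 days after the scheduled visit date (-3 days/+7 days". Protocol 8.14 and Table 5-2 place hematology, biochemistry, vital signs and the eC-SSRS at this visit, but no ECG.

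**Tables with a 140-day limit.** SAP 10.3 applies it to markedly abnormal laboratory values, the CTCAE grade summary and shift table, elevated liver tests and Hy's Law. SAP 10.5.1 applies it to markedly abnormal blood pressure. SAP 10.5.3 applies it to eC-SSRS incidence, "excluding any measurements that occurred prior to the first administration of study medication in AS0009 or more than 140 days after the last administration". SAP 10.5.2 has the same rule for QTc outliers.

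**Tables that also name the SFU Visit.** The elevated-liver-test table words its cut-off as follows: "140 days after the last administration of study medication) from all visits in AS0009 including those at AS0009 Laboratory Baseline, unscheduled, ET and SFU visits". The Hy's Law table has the same limit and draws on-treatment values "from all visits including those at AS0009 Laboratory Baseline, unscheduled, ET and SFU visits".

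**Outputs without a day limit.** The by-visit laboratory summaries in SAP 10.3 expressly include the SFU Visit. The vital-sign summaries in SAP 10.5.1 cover each visit, and SAP 2.2.1.3 lists the SFU among the vital-sign visits. The laboratory, vital-sign and eC-SSRS listings have no cut.

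**Adverse events.** SAP 10.2 uses the same figure: "Non-treatment emergent AEs are those with onset date after a 140-day period after the end date of study medication". Table 10-2 caps time at risk at 140 days and describes this as five half-lives.

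**The concern.** The limit and the target date of the visit are the same day, but the visit is allowed to run a week past it. A subject who attends on day 143 has complied with the protocol, yet none of that visit's results reaches the on-treatment tables. A subject with the same result on day 139 is counted. Nothing clinical separates the two.

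Long-term safety is the primary objective, and after Week 208 the SFU Visit is the only scheduled safety contact. The affected tables are those in which a reader would look for a neutrophil, liver or suicidality finding. They count subjects with at least one finding, or take each subject's worst grade, and SAP 3.1 bases percentages on the analysis set. Removing values can therefore only reduce the abnormal counts.

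The eC-SSRS has the most to lose. SAP 10.5.3 tabulates only the responses given since the last assessment, so an answer at the SFU Visit describes the interval back to the previous visit and not just that day. The by-visit eC-SSRS summary in Protocol 13.3.1 is not carried into the SAP. The incidence table is the only eC-SSRS summary, and a positive answer on day 143 would appear only in the listing.

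**Working it through.** **Inputs**
- SFU target: 20 weeks after the last dose (SAP 2.3).
- Window: 3 days early to 7 days late (Protocol section 8).
- Table limit: values more than 140 days after the last dose are out (SAP 10.3, 10.5.1, 10.5.3).
- Half-life: 28 days (SAP Table 10-1).
- Last dose for a completer: Week 204. Previous eC-SSRS: Week 208 (Protocol Table 5-2).

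**1. The plan's own figure.** Five half-lives: 5 × 28 = 140 days. SFU target: 20 × 7 = 140 days. The two agree exactly.

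**2. Permitted days.** Earliest 140 − 3 = 137; latest 140 + 7 = 147; number of days 147 − 137 + 1 = 11.

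**3. Split at the limit**

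| SFU day after last dose | Permitted days | In the on-treatment tables? |
|---|---|---|
| 137–140 | 4 | Yes |
| 141–147 | 7 | No |

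Excluded share of permitted days: 7 / 11 = 64%. Numbering both the visit and the limit with the dose day as Day 1 also gives 7 of 11. Mixing the two conventions, or reading the limit as day 140 or later, gives 8 of 11.

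**4. From days to subjects.** The documents do not say when SFU Visits actually fall. If all fall by day 140, no subject is affected. If all fall later, every subject with an SFU Visit is affected. An even spread over the window, which is an assumption, gives 64%.

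**5. What a late eC-SSRS answer covers.** On nominal dates, Week 208 is (208 − 204) × 7 = 28 days after the last dose. A visit on day *d* looks back over *d* − 28 days, of which 140 − 28 = 112 lie within the limit.
- Day 141: 112 / 113 = 99%
- Day 143: 112 / 115 = 97%
- Day 147: 112 / 119 = 94%

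At least 94% of the recall period lies within 140 days of the last dose, yet the whole answer is excluded. The Week 208 visit window of ±7 days shifts these figures slightly. Early terminators will have other intervals.

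**6. With the full SFU window accepted.** Permitted days excluded: 0 of 11.

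**The case against.** **The 140-day limit is deliberate.** It is tied to five half-lives and used consistently for TEAEs, event rates, time at risk and on-treatment assessments. A value taken beyond five half-lives can reasonably be called off-treatment, and a longer limit for assessments gives the SAP two meanings of on-treatment. This stands as a reason to leave the adverse-event rules alone. It is weaker for a scheduled visit whose target is day 140. Elsewhere the SAP treats the SFU by visit: SAP 9.1 keeps all SFU concentrations in the summary tables, and SAP 9.2 exempts the SFU from the antibody sampling window.

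**The liver-test and Hy's Law sentences are not strictly contradictory.** One filter is on time and the other on visit type, so an SFU value up to day 140 satisfies both. That is correct as logic. In effect, though, a visit named as included is excluded on most of its permitted days.

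**The values are not lost.** A reader might infer that the SAP discards every result after day 140. It does not: by-visit laboratory and vital-sign summaries and the listings retain them. SAP 10.3 also plans subject-number tables of markedly abnormal values at scheduled and unscheduled visits, with no day limit in that sentence. This narrows the concern to the incidence, grade and shift tables. It also means that a day-143 value could appear in one markedly-abnormal table and not in another.

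**The primary variables are largely untouched.** An event first reported at a day-143 visit but with onset by day 140 is still a TEAE, and Protocol 9.1.2 requires potential Hy's Law cases to be reported in any event. This stands.

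**Conclusion.** The point holds for the on-treatment incidence, CTCAE grade and shift tables for laboratory values (including liver enzymes and Hy's Law), markedly abnormal blood pressure and the eC-SSRS. On-time SFU results on 7 of 11 permitted days leave these tables, and the effect on abnormal counts runs one way. For laboratory values and blood pressure it is a modest misalignment, because the by-visit summaries remain. For the eC-SSRS it matters more, because only the listing remains.

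Three stronger readings are not supported:
- **That 64% of subjects or results are lost.** The 7 of 11 is a share of calendar days and becomes a share of subjects only under an even spread of visit dates.
- **That the follow-up from day 28 to day 140 is lost, and could be expressed in patient-years.** No laboratory, blood-pressure or eC-SSRS assessment is scheduled between Week 208 and the SFU Visit. What is at stake is one assessment per subject. Unscheduled laboratory and eC-SSRS values up to day 140 still count, and these tables report numbers and percentages, not exposure-adjusted rates.
- **That TEAE rates are biased.** Both the events counted and the time at risk stop at 140 days (SAP 10.1, 10.2, 10.2.2). Only events dated to days 141–147 fall outside, which follows from the stated definition.

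**What to change.** In SAP 10.3, 10.5.1 and 10.5.3, add one sentence: an SFU Visit attended within its protocol window, up to day 147 after the last dose, counts as on-treatment for assessment-based tables. Keep the 140-day limit for all other values, and leave the TEAE and time-at-risk definitions as they are. Say explicitly that the two rules differ and why, so that on-treatment is not read as one definition throughout.

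SAP 10.5.2 needs no change, since no ECG is done at the SFU Visit.

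The cost is SAP wording and a small programming change to the on-treatment flag. The downside is that a few values taken up to 7 days beyond five half-lives will be counted.

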10.4 Potential drug-induced liver Injury assessment

All PDILI events require immediate action, testing, and monitoring. The measurements and additional information required for the assessment of PDILI events when there is a reasonable possibility that they may have been caused by the study medication are included but not limited to those listed in [Table 10–11](#) and [Table 10–12](#).

PDILI laboratory results and additional PDILI information will be listed by treatment group at completion of AS0008 and subject. Where appropriate data will be included in the standard listings as indicated below:

- Family medical history, including any DILI-relevant medical conditions or inheritable disorders, start year and end year (or ongoing if applicable) (presented in the demographics section only for subjects with PDILI events)
- Study medication administration, including the date and time of most recent study medication administration, whether the subject discontinued study medication and the reason for discontinuation (presented in the compliance and drug concentration data section with a separate listing for PDILI events).
- Blood sample collection for PK including the variable, unit, date and time the sample was taken, and the result (presented in the compliance and drug concentration data section as part of the standard listing).
- Laboratory tests as detailed in [Table 10–6](#) (presented in the laboratory measurements section with a separate listing of PDILI events).
- Vital signs (presented in the safety analysis section as part of the standard listing)
- Lifestyle, including whether the subject has used alcohol in the past six months and whether the subject has used illicit drugs in the past six months (presented in the demographics section only for subjects with PDILI events).
- Hepatic event medical history, including any medical conditions which could have contributed to the suspected hepatic event prior to study entry will be listed together with all medical history data (presented in the demographics section).
- Symptoms of hepatitis and hypersensitivity, including whether the subject has taken any potentially hepatotoxic medications, whether the subject is experiencing symptoms of hepatitis, and whether the subject is experiencing symptoms of hypersensitivity (presented in the safety analysis section only for subjects with PDILI events).

Table 10–11: Additional potential drug-induced liver injury information

New or updated information
Concomitant prescription and over-the-counter medications (e.g. acetaminophen, herbal remedies, vitamins); dosages and dates should be included.

Pertinent medical history, including the following:

- History of liver disease (e.g. autoimmune hepatitis, nonalcoholic steatohepatitis or other “fatty liver disease”)
- Adverse reactions to drugs
- Allergies
- Relevant family history or inheritable disorders (e.g. Gilbert’s syndrome, alpha-1 antitrypsin deficiency)
- Recent travel
- Progression of malignancy involving the liver (Note: Metastatic disease to the liver, by itself, should not be used as an explanation for significant AST and/or ALT elevations.)

The appearance or worsening of clinical symptoms of hepatitis or hypersensitivity (e.g. fatigue, nausea, vomiting, right upper quadrant pain or tenderness, decreased appetite, abdominal pain, jaundice, fever, or rash)

Recent clinically significant hypotension or hypoxemia with compromised cardiopulmonary function

Alcohol and illicit drug use

Results of liver imaging or liver biopsy, if done

Results of any specialist or hepatology consult, if done

Any postmortem/pathology reports

ALT=alanine aminotransferase; AST=aspartate aminotransferase

Table 10–12: Potential drug-induced liver injury laboratory measurements

Virology-related	Hepatitis A IgM antibody
	HBsAg
	Hepatitis E IgM antibody
	HBcAb-IgM
	Hepatitis C RNA
	Cytomegalovirus IgM antibody
	Epstein-Barr viral capsid antigen IgM antibody (if unavailable, obtain heterophil antibody or monospot testing)
Immunology	Anti-nuclear antibody (qualitative and quantitative)
	Anti-smooth muscle antibody (qualitative and quantitative)

Table 10–12: Potential drug-induced liver injury laboratory measurements

	Type 1 anti-liver kidney microsomal antibodies (qualitative and quantitative)
Hematology	Eosinophil count
Urinalysis	Toxicology screen ^a
Chemistry	Amylase
	ALT, AST
	If total bilirubin $\geq 1.5 \times$ ULN, obtain fractionated bilirubin to obtain % direct bilirubin
	Serum CPK and LDH to evaluate possible muscle injury causing transaminase elevation
Additional	Prothrombin time/INR ^b
	Serum pregnancy test
	PK sample

ALT=alanine aminotransferase; AST=aspartate aminotransferase; CPK=creatine phosphokinase; HBcAb-IgM=hepatitis B core antibody-IgM; HBsAg=hepatitis B surface antigen; IgM=immunoglobulin M; INR=international normalized ratio; LDH=lactate dehydrogenase; PDILI=potential drug-induced liver injury; PK=pharmacokinetic; RNA=ribonucleic acid; ULN=upper limit of normal

^a For detecting substances (ie, amphetamines, benzodiazepines, opioids, marijuana, cocaine, phencyclidine, and tricyclic antidepressants), additional tests may be performed based on the Investigator's medical judgment and patient's history.

^b Measured only for subjects with ALT $> 8 \times$ ULN, elevations in total bilirubin, and symptoms of hepatitis or hypersensitivity. Hepatitis symptoms include fatigue, nausea, vomiting, and right upper quadrant pain or tenderness; hypersensitivity symptoms include eosinophilia ($> 5\%$), rash, and fever (without clear alternative cause).

